8.1 Enrolment

- There will be a study hub in the breast clinic making available study summary sheets, study information packs and a locked drop-box (for submission of study paperwork and saliva samples). BRCA-DIRECT posters will be on display at breast clinics.
- The patient will be made aware of the BRCA-DIRECT study via:
 - Recommendation and sign-posting towards the study from their doctor/specialist breast care nurse
 - The study-hub/poster
- A BRCA-DIRECT research genetic counsellor or research nurse will be available in clinic to answer questions.
- **COVID-19 addendum:** All COVID-19 related government guidelines applicable during the recruitment period of the study will be followed, (e.g regarding the wearing of personal protective equipment and social distancing).

8.1.1 Study resources/paperwork

Study Summary sheet

Patients will be invited to read a study summary sheet which outlines the study and asks those interested in participating to collect a study information pack and saliva sample kit. A section at the bottom of the sheet invites patients not interested in participating in BRCA-DIRECT to complete it anonymously, providing their reason why from the categories listed, and post it in the secure study drop box.

Study Information pack

Patients interested in participating will be given a study information pack containing:

- A front sheet
- Patient information leaflet
- Saliva kit and Expression of Interest form
- Study consent form and pre-paid envelope

Saliva sample collection and Expression of Interest

- Patients interested in participating in BRCA-DIRECT will be encouraged to provide a saliva sample in clinic, before leaving hospital (this avoids delays in testing, the need for an additional visit to hospital and the possibility of saliva samples being spoiled in transit).
- The patient will be asked to produce their own labelled saliva sample (following the instructions provided in the saliva sample kit).
- Healthcare professionals will be available to assist, if required.
- Patients will be asked to complete an Expression of Interest form, located inside the saliva sample kit, to provide their name and preferred contact details (mobile phone, email) and permission for their saliva sample to be stored while they decide whether to participate in BRCA-DIRECT.
- This form will be placed together with the saliva sample inside the sample bag and placed in the secure study drop box.
- Expression of Interest details and receipt of sample will be entered onto the BRCA-DIRECT study databases.

- If there are any problems with the saliva sample e.g. tube not sealed properly, damage etc., the local site genetic counsellor will contact the potential participant and arrange for another sample to be collected.
- **COVID-19 addendum:** In the event of COVID-19 regulations disallowing generation of saliva samples in clinic, we will enable participation in the study via (a) a saliva sample generated at home and posted back to ICR (b) supply of a blood sample in clinic (if the patient is having routine bloods taken in clinic). Thus, we shall make available in clinic two types of study packs (a) “home-saliva study-pack”, including tube for home saliva collection and secure sample postal kit and (b) “blood study-pack”, including bottle and forms to be handed to phlebotomy. The “home-saliva study-pack” can also be posted out to potential participants undergoing telephone consultation. These pathways offer flexibility regarding (i) prohibition of saliva generation in hospital clinic setting (ii) discontinuation of laboratory analysis of saliva samples (iii) additional reduction in face-to-face appointments (see participant pathway flowchart COVID-19 contingency).

Patient information leaflet and consent to join BRCA-DIRECT

Potential participants can take home their patient information leaflet and study consent form. The telephone number of the local site research genetic counsellor is listed in the patient information leaflet. A study telephone hotline, manned by the local site research genetic counsellor, will be available to all participants ahead of recruitment to address any questions they have about the study. Those wishing to join the study are instructed to sign and return the study consent form in the pre-paid envelope provided. This form also contains a section for patients to complete and return if they don't want to participate in the study.

Some patients may choose to read the patient information leaflet and sign their study consent form whilst in clinic. This will be permitted because participants will not be contacted by the BRCA-DIRECT study databases for at least 24 hours. The study interface contains a link to take a participant to a study withdrawal screen, which will be available at all stages of participation.

All participants will receive a copy of their signed study consent form via a secure method (encrypted email or post).

If a signed study consent form is not received from a potential participant who provided a saliva/blood sample, the BRCA-DIRECT study system will send four consecutive reminders 1, 7, 12 and 17 days after the sample was deposited, using the patient's preferred contact (mobile phone/email). If signed consent is not received after six weeks, the temporarily stored sample and Expression of Interest form will be destroyed.

8.1.2 Baseline checks and 24 hour pause

On receipt of a signed study consent form, the local site will confirm the patient's eligibility and enter details required for study conduct onto the BRCA-DIRECT databases. If, in exceptional circumstances, a patient is found to be ineligible for the study, they will be telephoned by their consultant or the study genetic counsellor.

After 24 hours, the participant will be sent a link to the BRCA-DIRECT study platform interface. This link enables the participant to:

- Withdraw from the study if they have changed their mind
- Progress through the BRCA-DIRECT study

8.2 Commencing participation in BRCA-DIRECT

Participants will complete digitally:

- A cancer family history questionnaire
- Intolerance of Uncertainty questionnaire
- STAI Y-1/Y-2 state/trait anxiety questionnaires
- Knowledge questionnaire

If baseline questionnaires are not completed, an SMS/email reminder to complete them will be sent to the participant 1, 2 and 3 days after receiving the initial link to BRCA-DIRECT study interface.

8.3 Delivery of information about genetic testing for BRCA genes BRCA1, BRCA2, PALB2

Participants will be randomised 1:1 to:

(i) **Receiving digital information about genetic testing for BRCA genes via the BRCA-DIRECT study interface**

- Participants will be able to scroll forwards and backwards through the information visiting links etc.
- The BRCA-DIRECT study system will record participant activity to confirm that they have visited the information before proceeding to the next stage of the study.
- Participants will be able to call the telephone hotline with queries or if they would like further information.
- The final screen will provide a link to access the digital 'BRCA-test consent' form. Participants will be able to call the telephone hotline if they would like to be taken through the clauses on the form.

Or

(ii) **Receiving a current standard of care telephone consultation with a genetic counsellor**

- Participants will be instructed to book an appointment with a genetic counsellor via a digital calendar located on the BRCA-DIRECT interface. They will be asked to book an appointment within the next three working days, if possible.
- At the end of the consultation, the genetic counsellor will inform the participant that a digital 'BRCA-test consent' form is available to be completed and signed via the BRCA-DIRECT interface. An explanation of the individual clauses within the form will be given.
- The genetic counsellor will log the consultation as completed and enable the digital consent form.
- A standard summary of the consultation will be sent via post to the participant.

If a participant does not book a genetic counselling appointment or commence viewing the digital pre-test information, an SMS/email reminder will be sent 1, 2 and 3 days after notification of the randomised allocation was received.

If a participant is unavailable during the booked appointment time they will be invited to book another appointment three additional times by the BRCA-DIRECT study system.

8.4 Consent to proceed to genetic testing

- For both arms, if a participant decides to proceed with the genetic test they will sign a digital 'BRCA-test consent' form, which will be formatted to BSGM (British Society of Genomic Medicine) standards. All participants will receive a copy of their signed BRCA-test consent form via secure email/post.
- The participant will have two days following test-consent to reverse the decision to proceed with the BRCA-test. Beyond those two days, the test will proceed.
- If a signed 'BRCA-test consent' form is not received from a participant, the BRCA-DIRECT study system will send three reminders 1, 2 and 3 days after the participant viewed the digital pre-test information or had a telephone consultation with a genetic counsellor.
- If signed consent is not received after 8 weeks, the temporarily stored sample and Expression of Interest form will be destroyed and the participant will be withdrawn from the study.
- If a participant subsequently decides to proceed to genetic testing during the active period of the study, and is willing to provide another saliva/blood sample, this will be discussed with the patient and a test conducted if feasible.

8.5 Assessment of knowledge and anxiety following consent for genetic testing to proceed

24 hours after signing consent for the genetic test to proceed, participants will complete digitally:

- Knowledge questionnaire
- STAI Y-1 anxiety questionnaire

If these questionnaires are not completed, an SMS/email reminder to complete them will be sent to the participant 4, 5 and 6 days after signing consent for the genetic test to proceed.

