| Study objectives | 
Primary Objective To evaluate whether digital delivery of pre-test information for BRCA-testing in breast cancer patients is non-inferior to current standard practice of 1:1 delivery from a healthcare professional regarding uptake of genetic test.
 
Secondary Objectives
 
 • To assess knowledge about genetic testing for BRCA genes, following delivery of pre-test information, in the two allocated groups • To assess anxiety following delivery of pre-test information, and test results, in the two allocated groups 
Additional secondary objectives:
 
 • To assess uptake of digital genetic testing • To compare 'Test-offer-to-results' time between BRCA-DIRECT digital model and contemporaneous clinical service • To evaluate uptake of telephone helpline • To evaluate Healthcare professional satisfaction with BRCA-DIRECT digital model • To evaluate Patient satisfaction with BRCA-DIRECT digital model |
| Centres | 
Royal Marsden NHS Foundation Trust (RMH)
 
Manchester University Hospitals NHS Foundation Trust (MFT)
 |
| Study Endpoints | 
Primary Outcome Uptake of genetic testing for BRCA genes in women with a diagnosis of breast cancer
 
Secondary Outcomes
 
 • Knowledge about genetic testing for BRCA genes (12-point knowledge test administered Day 1 following pre-test information) • Anxiety (Intolerance of Uncertainty and STAI Y-1/Y-2 state/trait anxiety) 
Additional secondary outcomes:
 
 • Potential participant decline on account of lack of digital access • 'Test-offer-to-results' time |

| | |
|--------------------|--|
| | 
 ○ Study compared to audit of contemporaneous timings from referral to results at participating centres ● Helpline usage 
 ○ Evaluate proportion of patients receiving digital pre-test information who require 1:1 discussion via helpline ● Healthcare professional satisfaction ● Patient satisfaction |
| Inclusion criteria | 
 ● Diagnosis of invasive breast cancer or high-grade ductal carcinoma in situ (DCIS) ● Female ● Aged 18 years or over ● Access to smartphone or email + internet ● Good comprehension of the English Language |
| Exclusion criteria | Previous testing for BRCA1/2 |

Table of Contents

| | |
|--|-----------|
| Summary of Investigators | 2 |

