2.3 Secondary Objectives

- To assess knowledge about genetic testing for BRCA genes, following delivery of pre-test information, in the two allocated groups
- To assess anxiety following delivery of pre-test information, and test results, in the two allocated groups

This study will be conducted in compliance with the protocol, standard operating procedures, policies, local R&D management guidance, Good Clinical Practice including the Research Governance Framework 2005 (2nd edition) and other applicable regulatory requirements as amended from time to time.

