7 MEASUREMENT OF STUDY ENDPOINTS

Uptake of genetic testing will be measured as the proportion of participants proceeding to genetic testing following delivery of pre-test information either digitally, or via a telephone consultation with a genetic counsellor.

Knowledge will be assessed using a study-specific questionnaire, designed to test knowledge in key areas of genetic susceptibility awareness for breast/ovarian cancer. The questionnaire has been (i) developed using two previously published questionnaires developed to evaluate knowledge following delivery of genetic counselling information about increased risk for breast cancer, (ii) tested on 3 clinical genetics professionals, 3 oncologists, and (iii) reviewed by our PPI panel comprising patients with breast cancer and patients who have undergone BRCA-testing^{40, 54}.

Anxiety will be measured using the Spielberger state-trait anxiety inventory⁵⁵ and the short form Intolerance of Uncertainty scale⁵⁶.

The Spielberger state-trait anxiety inventory consists of two self-administered, 20-item questionnaires, with each item rated on a four-point Likert scale. It assesses anxiety proneness (trait) and the current state of anxiety change (state). The Trait anxiety is measured only once and the State at each time point. High STAI scores signify greater anxiety.

Research suggests that intolerance of uncertainty may be very important in understanding worry and may play a key role in the etiology and maintenance of worry. Evidence for the connection between intolerance of uncertainty and worry comes from studies that established that worriers possess a number of characteristics that set them apart from non-worriers. For example, worriers have been

shown to require more information before arriving at a decision ⁵⁷. The need for additional information may be a means for lowering the level of uncertainty.

Decline on account of lack of access to digital interface will be assessed from completed anonymous study summary forms posted into the secure study hub drop boxes.

'Test-offer-to-results' time (study compared to audit of timings under current pathways at participating centres)

Helpline usage will be assessed from a central log of the number, content and duration of calls made to the genetic counsellor telephone hot line.

Healthcare professional satisfaction will be assessed using a study specific survey

Patient satisfaction will be measured using a digital study specific survey.

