8.9.1 Schedule of patient reported outcome assessments

| Time point | STAI Trait (Y-2) | STAI State (Y-1) | Intolerance of Uncertainty | Knowledge Score | Participant Satisfaction Survey (+ optional telephone interview) |
|---|------------------|------------------|----------------------------|-----------------|--|
| T0 - Baseline | ✓ | ✓ | ✓ | ✓ | |
| T1 – 24 hours after giving consent for genetic test to proceed | | ✓ | | ✓ | |
| T2 – 7 days after notification that test results are available | | ✓ | | | ✓ |
| T3 – 28 days after notification that test results are available | | ✓ | | ✓ | ✓ (reminder if not done at T2) |

All calls to the telephone hotline will be logged on BRCA-DIRECT system by the genetic counsellor who took the call (content and duration of call).

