12.3 Internal pilot

When 120 participants have been enrolled (60 participants in each arm), recruitment will pause and study data will be reviewed as follows:

Recruitment:

Actual recruitment will be compared with predicted recruitment. Any potential barriers to recruitment will be identified through liaison with local sites and information collected on Study Summary Sheets completed by patients who were not interested in taking part in BRCA-DIRECT.

Retention:

Retention will be evaluated by reviewing:

- Participant initiated withdrawal
- Drop out as a result of non-completion of study tasks

Where participants have provided a reason why they wished to withdraw, these will be examined for any consistent themes. Drop out time point will be examined to search for any problems within the BRCA-DIRECT study pathway.

Compliance:

Timeliness of completion of study tasks throughout the participant pathway will be compared to expected timelines, to identify any non-random delays at study timepoints. Data from the Participant Satisfaction Survey and telephone interviews (user feedback) will be examined to assist with identifying the cause of any such delays.

Completion of the full pathway will be compared to expected compliance. If compliance is less than expected, reasons why will be identified and resolved, where possible.

Preliminary review of participant knowledge following receipt of pre-test information and consent for genetic test:

We aim to provide participants with a clinician independent means of receiving information about genetic testing for BRCA genes that is not inferior to current practice. Review of Knowledge questionnaire data, user feedback and consent for genetic testing in 120 participants will highlight any major differences between the study arms that may require further investigation and resolution before recruitment recommences.

Data completeness:

Individual questionnaires will contain checks to prevent incomplete data. Non- completion of questionnaires will be examined at each study timepoint to search for any problematic timepoints. Reasons for non-completion of questionnaires will be identified and resolved, where possible.

Knowledge questionnaire and Participant Satisfaction Survey:

Pooled data will be examined to search for any consistent themes that may require resolution before recruitment recommences.

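### T1 knowledge and anxiety are collected only from women who sign test consent, which conflicts with the stated objectives and with the 0% attrition given for STAI T1 in the power table

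*Combined protocol and SAP*

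**What the plan says.** Every participant completes the knowledge questionnaire and the "STAI Y-1/Y-2 state/trait anxiety questionnaires" at baseline (section 8.2). The next assessment, T1, depends on test consent. Section 8.5 reads "24 hours after signing consent for the genetic test to proceed, participants will complete digitally", and its reminders also count from signing. The schedule in section 8.9.1 repeats the anchor: "24 hours after giving consent for genetic test to proceed". The pilot check in section 12.3 is headed "Preliminary review of participant knowledge following receipt of pre-test information and consent for genetic test". T2 and T3 are timed from test results.

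Other parts of the protocol describe the outcome differently. The synopsis lists a "12-point knowledge test administered Day 1 following pre-test information". Section 2.3 states the objective as "To assess knowledge about genetic testing for BRCA genes, following delivery of pre-test information, in the two allocated groups", with parallel wording for anxiety.

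For a woman who does not sign, section 8.4 begins "If signed consent is not received after 8 weeks" and goes on to sample destruction and withdrawal from the study. Section 8.4 also lets a signer reverse her decision within two days. On the primary outcome, section 7 says "Uptake of genetic testing will be measured as the proportion of participants proceeding to genetic testing following delivery of pre-test information".

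The table in section 12.1 assumes 90% uptake in both groups. It gives STAI T1 0% attrition and 1000 available, STAI T2 10% and 900, STAI T3 20% and 800, and Knowledge T1 20% and 800.

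Section 12.4 makes the per-protocol analysis primary, adds a complete-case intention-to-treat analysis, and leaves multiple imputation optional. Continuous outcomes go into a mixed model with baseline score, arm, centre and time point as fixed effects. No arm-by-time term is listed.

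**The concern.** Signing happens after randomisation and after the information whose effect is being compared. If digital and telephone delivery lead different kinds of women to stop before signing, a comparison of signers is not a comparison of the groups as randomised. The women left out may be those whom the information served least well. They have baseline scores only. Because baseline enters section 12.4 as a covariate, they contribute nothing to the T1 estimate unless the optional imputation is used, and that would have only baseline data to draw on. The pilot's by-arm knowledge check has the same limit.

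The power table also ignores the consequence of its own uptake assumption. If one woman in ten does not proceed, STAI T1 cannot have complete data. Two questionnaires sent together cannot sensibly have different attrition without a stated reason.

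**Working it through.** **Inputs (section 12.1):** 1000 women randomised 1:1, 90% uptake per arm; STAI SD 13.5, margin 3, one-sided 0.025; knowledge SD 1.55, margin 1.40.

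**1. Reproduce the plan.** n per arm = 2 × 13.5² × (1.96 + 0.8416)² / 3² = 318, total 636, as stated. With SE = 13.5 × √(2/n per arm) and power = Φ(3/SE − 1.96), 1000 women give SE 0.854 and power 94.0%, inside the stated 90-95%.

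**2. Apply the plan's own uptake.** 1000 × 0.90 = 900 women proceed. Those who sign and then reverse also receive T1, so signers may slightly exceed 900. Zero attrition would need all 1000 to sign and respond.

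| STAI T1 available | SE | Power |
|---|---|---|
| 1000 | 0.854 | 94.0% |
| 900 | 0.900 | 91.5% |
| 800 (the plan's Knowledge T1 number) | 0.955 | 88.2% |
| 636 | 1.071 | 80.0% |

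Power of 80% needs 636/900 = 71% of signers to respond.

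**3. Non-response left in each row, against 900.** T2: 1 − 900/900 = 0%. T3 and Knowledge T1: 1 − 800/900 = 11%. If the 10% and 20% were meant as losses on top of non-uptake, T2 and T3 would have 810 and 720 women, with power 88.5% and 84.6%.

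**4. Pilot.** 60 × 0.90 = 54 women per arm would inform the knowledge check.

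**5. Possible selection bias, STAI.** The documents give no figure for how non-signers differ. Assume a fraction q = 0.10 of non-signers per arm, differing from signers by D = 5 or 10 points in one arm only, and a T0–T1 correlation r of 0.5 or 0.7. This is a single-time-point, baseline-adjusted illustration, not the repeated-measures model of section 12.4.
- Baseline fully explains the gap: bias 0.
- The full gap is present at T0 and T1: bias = qD(1 − r), which is 0.25 and 0.50 (r = 0.5) or 0.15 and 0.30 (r = 0.7).
- The gap arises only after the information: bias = qD = 0.5 and 1.0.
- Non-signers differ equally in both arms: bias 0.

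**6. Tipping point, same illustration at 900 women.** Adjusted SE = 0.900 × √(1 − r²) = 0.779 (r = 0.5) or 0.643 (r = 0.7). The shift needed in digital-arm non-signers alone to lose non-inferiority is (3 − observed difference − 1.96 × SE)/0.10. At an observed difference of 0 this is 14.7 or 17.4 points; at an observed 1 point it is 4.7 or 7.4.

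**7. Knowledge.** If the lowest-scoring 10% of one arm is missing, bias = 1.55 × 0.1755/0.9 = 0.30. With opposite selection in the two arms it is 2 × 0.30 = 0.60. Both are well below 1.40.

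**The case against.** These are secondary outcomes for which section 12 says the study is not primarily powered. The table error leaves power at 91.5% with 900 women, inside the stated band. The STAI bias rests wholly on assumed gaps and correlations and matters only if the result lies near the margin. Section 12.3 also reviews consent, drop-out point and questionnaire non-completion, so the pilot does not rest on signers' scores alone. Section 12.4 plans a CONSORT flowchart, allows imputation and defers detail to a full SAP. All of this stands. It limits the weight of the point, but it neither removes the conflict between the passages nor makes T1 a comparison of the randomised groups.

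It is also fair to object to the obvious remedy of sending T1 to every woman soon after the information. Consent stays open for 8 weeks, so a knowledge or anxiety questionnaire sent to undecided women acts as a further prompt and could itself move uptake, the primary outcome. That objection is accepted in the fix.

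A reader might infer that the false non-inferiority rate is badly inflated. In the illustration above, Φ(−1.96 + 1.0/0.643) is about 34%. That needs a 10-point gap in one arm only, arising entirely after the information, with r = 0.7, in a model that is not the planned one. The documents support none of those inputs.

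**Conclusion.** The point holds as a mismatch between objective, timing and power table, and as a limit on what T1 can describe. As written, T1 compares signers. The STAI T1 entry of 0% and 1000 cannot be right under 90% uptake: attrition is at least about 10%. It is also inconsistent with the 20% given for Knowledge T1. With 800 women, STAI power is 88.2%, below the stated band but above 80%. T2's 900 is used up by non-uptake alone.

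Three stronger readings are not supported:
- **STAI T1 is underpowered.** It is not: 636 women suffice for 80% power.
- **T1 is conditioned on the primary outcome itself.** Signing leads to uptake but is not identical to it, because uptake is proceeding to testing and consent can be reversed.
- **The T1 results will be biased.** Bias may be zero and can go either way. The illustrative 0 to 1.0 STAI points assumes 10% non-signers differing by 5 to 10 points in one arm only. Knowledge non-inferiority is barely at risk.

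That nothing more is collected after the 8-week withdrawal is partly inference, since section 8.12 mainly concerns withdrawal at the participant's wish. Either way, no questionnaire is scheduled for a woman who does not sign.

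**What to change.** 1. **Section 12.1 table.** Restate STAI T1 as at least 10% attrition and at most about 900 available. Use one attrition figure for STAI T1 and Knowledge T1. Make the T2 and T3 figures cover both non-uptake and non-response, and restate the power.
2. **Wording.** Reconcile the synopsis and sections 2.3, 8.5, 8.9.1 and 12.3. If the consent trigger is kept, say plainly that T1 is a comparison among signers.
3. **SAP.** For both the per-protocol and intention-to-treat analyses, specify a T1-specific arm contrast, with a sensitivity analysis that shifts the T1 scores of unmeasured non-signers separately by arm. Report by arm how many received the information, signed, reversed and completed T1. Sections 8.3 and 16.2 say the platform records receipt of the information.

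These are changes to documents and reporting only, and section 12.4 says the full SAP is still to be written.

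Do not send questionnaires to undecided women while consent is open. If non-signers are to be measured, do it once, at the close of the 8-week window and before withdrawal. That costs one platform trigger and an amendment. Its downsides should be named: late measurement, probably low response, and a different clock from signers. Women who never receive the information or who withdraw themselves would stay unmeasured, so fewer than about 100 are recoverable.
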